5.7.5. Physical Examination

The subject will undergo an evaluation of all major body systems, including the measurement of height and weight. Physical examinations will be performed at the Screening Visit and at Visits -3, -2, -1, TP1-EXT, EOS, 1, 3, 5, 7, 9, 11, 13, at all subsequent quarterly Study Visits, and at the Safety Follow-up Visit.

5.7.6. Electrocardiogram

A 12-lead Electrocardiogram (ECG) will be performed to evaluate potential study drug-induced QT prolongation potential at the Screening Visit, at all Study Visits, at the End of Study Visit, and at the Safety Follow-up Visit. At Visits 1 and 3, ECG will be performed 5 times: before administration of both Sodium Cridanimod and megestrol acetate, and at 15, 60, 120, and 360 (\pm 5) minutes after administration of Sodium Cridanimod. ECGs at all other visits will be performed only once, prior to administration of both Sodium Cridanimod and megestrol acetate.

For all ECGs performed after the first dose of Sodium Cridanimod, any clinically significant changes compared with the ECG recorded at the Screening Visit must be reported as an AE. All ECG intervals (QT, QTcB, QTcF, PR, QRS, and RR) will be reported in the eCRF.

5.7.7. Patient Diary

At all visits following the Screening Visit, the subject will be provided with Patient Diaries and asked to record their daily doses of megestrol acetate (including those taken in clinic during a study visit). In addition, subjects are to record any AEs and concomitant medications in the diary. Diaries will be completed by the subjects until they exit the study at the End of Study Visit or the Safety Follow-up Visit. Subjects will be instructed to return their completed diaries at each Study Visit and new diaries will be provided to the subject.

5.8. Optional Sub-Study Procedures

To address an important translational objective, subjects will have the ability to consent to participate in an optional sub-study. Participation in this sub-study is completely voluntary and will not affect the subject's ability to participate in the study. Participation in this study will undergo additional study procedures as outlined below.

5.8.1. Optional Pharmacokinetic (PK) Sub-Study

An important objective of this study is to investigate the possible pharmacokinetics of megestrol acetate when administered alone (Treatment Period 1), and the pharmacokinetic drug-drug interactions of Sodium Cridanimod and megestrol acetate when administered together (Treatment Period 2). To accomplish this objective, certain subjects will be enrolled to participate in an optional Pharmacokinetic Sub-Study.

For these subjects, additional blood samples will be taken as follows:

- Treatment Period 1: Study Visit -3, before administration of megestrol acetate, and 1, 2, 3, 4, 6, 24, 48, 72 and 96 hours (all times +/- 2 minutes) after administration. ***Subjects who are PrR negative will not participate in this portion of the PK Sub-Study.***
- Treatment Period 2: Study Visit 1, before administration of both Sodium Cridanimod and megestrol acetate and at 15, 30, 45, 60 and 90 minutes, 2, 3, 4 and 6 hours (all times +/- 2 minutes) after administration. Blood samples will additionally be taken on Days 3, 7, 10, 56 (Visit 3) and Day 84 (Visit 4) prior to the administration of both Sodium Cridanimod and megestrol acetate. Administration of the study drugs should be timed as close as possible on PK days, preferably within 5 minutes or less. Timing of the post dose PK blood sample collection should be based on the Sodium Cridanimod dose.

Blood samples will be analyzed in a central laboratory using standard analysis methods.

5.9. Adverse Events and Other Safety Aspects

5.9.1. Definition of Adverse Events

An AE is any untoward medical occurrence in a subject administered a medicinal product and which does not necessarily have to have a causal relationship with treatment in Treatment Period 1, 2 through either the End of Study Visit or the Safety Follow-up Visit. An AE can therefore be any unfavorable and unintended sign (for example, an abnormal laboratory finding), symptom, or

disease temporally associated with the use of a medicinal product, whether or not considered related to this medicinal product.

For the purposes of this protocol, an AE is any undesirable sign(s), symptom(s) or worsening of pre-existing condition(s) occurring after the signing of the informed consent through the final study visit, even if the event is not considered to be related to the study drug. No AEs information will be collected following the End of Study Visit/Safety Follow-up Visit.

AEs do not include the following:

- The disease being studied, or the expected progression, signs or symptoms (including laboratory values) of the disease being studied, unless it is more severe than expected for the subject's condition. Disease progression or symptoms related to disease progression will not be considered AEs.
- Pre-existing disease or medical conditions that does not worsen from those reported at Screening.
- Hospitalizations for elective surgery unless the event meets other criteria as an SAE such as "prolonged hospitalization".
- Hospital admissions for social or convenience reasons where an AE does not occur.
- Medical or surgical procedures such as surgeries and transfusions. These are treatments for an AE resulting in the procedure. The underlying AE should be reported as the event, not the procedure.
- Elective treatment of a pre-existing disease or medical condition that did not worsen or result in AEs, e.g., hospitalization for chemotherapy for cancer.
- Overdose of either study drug or any concomitant medication without any signs or symptoms.

Intercurrent illnesses or injuries should be regarded as AEs. Abnormal results of diagnostic procedures are considered to be AEs if the abnormality:

- is considered by the Investigator to be of clinical significance
- results in study withdrawal
- is associated with clinical signs or symptoms
- leads to additional treatment or to further diagnostic tests

An AE is "unexpected" when the nature, severity, specificity, or outcome is not consistent with the term or description used in protocol related documents including the Investigator brochure, product labeling (e.g. Package Insert or Summary of Product Characteristics), protocol and IEC/IRB approved informed consent form. If an Investigator is uncertain whether an AE is expected or unexpected, the AE should be reported as unexpected.

The outcome of each AE should be assessed as follows:

- Fatal: Subject has died due to AE
- Not Recovered/Not Resolved: AE is ongoing
- Recovered/Resolved: AE is no longer present
- Recovered/Resolved with sequelae: AE has resolved but the subject retains a condition that is the consequence of the AE

- Recovered/Resolving: AE is in the process of recovering
- Unknown: Outcome of the AE is not known because the subject did not return for follow-up and attempts to obtain follow-up were unsuccessful

The Investigator will assess subjects for AEs at each study visit through the End of Study Visit/Safety Follow-up Visit. All AEs observed or reported after the subject has provided informed consent must be recorded in the source data and reported on the eCRF regardless of causal relationship. The nature of each AE, date of onset, outcome, severity, actions taken with respect to dosage, and relationship to study drug should be assessed and recorded. Any changes to study drug dosing or any medical treatment should be recorded in the source and appropriate eCRFs. AEs documented at a previous assessment as 'ongoing' should be reviewed at subsequent visits as necessary until resolved.

All related signs, symptoms, and abnormal diagnostic procedures results should be grouped as a diagnosis whenever possible. All AEs will be assessed for severity, seriousness and causality by the Investigator.

AEs that do not meet the criteria for expedited reporting will be documented in the eCRF and reported in the final clinical study report.

5.9.2. Definition of Serious Adverse Events

An SAE is defined as any untoward medical occurrence or effect that, at any dose:

- Results in death;
- Is life-threatening*;
- Requires hospitalization or prolongation of hospitalization;
- Results in persistent or significant disability or incapacity;
- Is a congenital abnormality or birth defect;
- Other medically important event

Medical judgment should be exercised in deciding whether an AE/reaction is serious in other situations. Important AEs/reactions that are not immediately life-threatening, or do not result in death or hospitalization but may jeopardize a subject, or may require intervention to prevent one of the other outcomes listed in the definition above should also be considered serious.

** "Life-threatening" in the definition of "serious" refers to an event in which the subject was at risk of death at the time of the event; it does not refer to an event which hypothetically might have caused death if it were more severe.*

5.9.3. Criteria for Causal Relationship

Table 14. The causality of each AE should be assessed using one of the following terms:

Causal Relationship* to the Study Drug	Criteria for Causal Relationship
Related	AE occurring in a plausible time relationship to drug administration, and which cannot be explained by concurrent disease or other drugs or chemicals.
Possibly Related	AE occurring with a reasonable time sequence to administration of the drug, unlikely to be attributed to concurrent disease or other drugs or chemicals.
Unlikely Related	AE occurring with a reasonable time sequence to administration of the drug, but which could also be explained by concurrent disease or other drugs or chemicals.
Not Related	AE with a temporal relationship to drug administration which makes a causal relationship improbable, and in which other drugs, chemicals or underlying disease provide plausible explanations.

*Definitions with basis in *Clinical Data Acquisition Standards Harmonization (CDASH), ICH E2B*.

For data analysis and SAE reporting purposes, any AEs classified as 'unlikely related' will be regarded as 'not related' to study drug. AEs classified as 'possibly related' will be regarded as 'related' to the study drug.

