15.1 Adverse Events

An AE is any untoward medical occurrence in a subject or clinical investigation subject administered a pharmaceutical product that does not necessarily have a causal relationship with this treatment. An AE can therefore be any unfavorable and unintended sign (including a clinically significant abnormal laboratory finding), symptom or disease temporally associated with the use of a pharmaceutical product, whether or not considered related to the pharmaceutical product. AEs may include the onset of new illness and the exacerbation of pre-existing conditions.

For the purposes of this protocol, an AE is any undesirable sign(s), symptom(s) or worsening of pre-existing condition(s) occurring after the signing of the informed consent through the final study visit, even if the event is not considered to be related to the study drug. No AEs information will be collected following the Safety Follow-Up Visit. The nature of each AE, date of onset, outcome, severity, actions taken with respect to dosage, and relationship to study drug will be assessed and recorded.

An AE is “unexpected” when the nature, severity, specificity, or outcome is not consistent with the term or description used in protocol related documents including the Investigator brochure, product labeling

(e.g. Package Insert or Summary of Product Characteristics), protocol and Independent Ethics Committee (IEC)/ Institutional Review Board (IRB) approved informed consent form. If an Investigator is uncertain whether an AE is expected or unexpected, the AE should be reported as unexpected.

The outcome of each AE should be assessed as follows:

- Fatal: Subject has died due to AE
- Not Recovered/Not Resolved: AE is ongoing
- Recovered/Resolved: AE is no longer present
- Recovered/Resolved with sequelae: AE has resolved but the subject retains a condition that is the consequence of the AE
- Recovered/Resolving: AE is in the process of recovering
- Unknown: Outcome of the AE is not known because the subject did not return for follow-up and attempts to obtain follow-up were unsuccessful

The causality of each AE, with respect to each study drug separately, should be assessed using one of the following terms:

- Related: AE occurring in a plausible time relationship to drug administration, and which cannot be explained by concurrent disease or other drugs or chemicals.

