- Possibly Related: AE occurring with a reasonable time sequence to administration of the drug, unlikely to be attributed to concurrent disease or other drugs or chemicals.
- Unlikely Related: AE occurring with a reasonable time sequence to administration of the drug, but which could also be explained by concurrent disease or other drugs or chemicals.
- Not Related: AE with a temporal relationship to drug administration which makes a causal relationship improbable, and in which other drugs, chemicals or underlying disease provide plausible explanations.

For data analysis and Serious Adverse Event (SAE) reporting purposes, any AEs classified as 'unlikely related' will be regarded as 'not related' to study drug. AEs classified as 'possibly related' will be regarded as 'related' to the study drug.

The severity of all AEs should be graded in accordance with the NCI-CTCAE Version 4:

- 1 – Mild: Does not hamper daily activities
- 2 – Moderate: Hampers daily activities

3 – Severe: Makes daily activities impossible

4 – Life-Threatening: Imminent risk of death

5 – Death

Disease progression or symptoms related to disease progression will not be considered AEs.

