15.3 Adverse Events Listings

All AEs, SAEs, AEs leading to treatment period discontinuation, and AEs with outcome of death, including the applied coded terms, will be presented in subject listings. Each AE listing will include onset and resolution date, coded term, SOC, PT, relatedness, seriousness, severity, outcome and action taken. Treatment-emergent events will be flagged in these listings.

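### Does counting 'unlikely related' adverse events as 'not related' distort the safety listings?

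*Protocol*

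**What the plan says.** Table 14 in protocol section 5.9.3 gives four causality terms, and SAP section 15.1 carries the same four definitions. For 'Unlikely Related' the timing is reasonable, "but which could also be explained by concurrent disease or other drugs or chemicals". 'Not Related' begins from the opposite position on timing: "AE with a temporal relationship to drug administration which makes a causal relationship improbable", and it also requires plausible other explanations.

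Two mapping sentences follow. The first is "For data analysis and SAE reporting purposes, any AEs classified as 'unlikely related' will be regarded as 'not related' to study drug". The second is "AEs classified as 'possibly related' will be regarded as 'related' to the study drug". SAP section 15.1 repeats both, the first as "any AEs classified as 'unlikely related' will be regarded as 'not related' to study drug".

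The column heading of Table 14 speaks of one drug, "Causal Relationship* to the Study Drug". The SAP asks for a rating per drug: "The causality of each AE, with respect to each study drug separately, should be assessed using one of the following terms".

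SAP section 15.3 sets the content of the listings: "Each AE listing will include onset and resolution date, coded term, SOC, PT, relatedness, seriousness, severity, outcome and action taken". SAP sections 3.2 and 20 confine safety reporting to listings, apart from one table of QTc categories. SAP section 1 says that its methods replace those of the protocol, so the tabulated summaries by relationship in protocol section 7.5.1 are no longer planned.

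**The concern.** An event with compatible timing and a possible other cause meets the definition of 'Unlikely Related' and fails that of 'Not Related'. The mapping nevertheless gives it the 'not related' label. Patients here have advanced cancer and, in Treatment Period 2, take two study drugs together, with lidocaine in each injection. Another possible explanation will often be at hand, so the 'unlikely' class could be large.

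Safety is a secondary objective, and the listings are almost all that will be reported on it. If the relatedness column held only the grouped label, a reader could not tell an event whose timing fits the drug from one whose timing argues against it. The mapping also extends to the reporting of serious events, so one might fear that a causality-dependent report would be missed.

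**Working it through.** No formula or design figure is involved. The check sets the definitions side by side, applies the mapping, and follows the result into each place where relatedness is used.

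**1. Definitions and mapping (protocol Table 14; SAP section 15.1)**

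| Recorded term | Timing | Other explanation | Group after mapping | Meets the strict definition of that label? |
|---|---|---|---|---|
| Related | plausible | excluded | related | yes |
| Possibly Related | reasonable | unlikely | related | no: another cause is not excluded |
| Unlikely Related | reasonable | possible | not related | no: timing is not improbable |
| Not Related | improbable | plausible | not related | yes |

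Three of the four terms have compatible timing. Two of those three end as related and one as not related. The mismatch is real, but it appears on both sides of the cut. Any two-way split of a four-term scale puts the middle terms under labels whose narrow definitions they do not meet. The documents say that these terms will be regarded as the end terms, which is a grouping rule and not a claim that the definitions coincide.

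**2. Effect on the number of related events**

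Let R, P, U and N be the numbers of events recorded under the four terms, in table order.

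- Labelled 'related' as recorded: R.
- After the 'unlikely' step alone: still R, because U was outside the related group before and stays outside. Change: R − R = 0.
- After both steps: R + P. Change: (R + P) − R = P, which is zero or positive.

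The related count would be lower only in comparison with a different cut, R + P + U, and the shortfall would then be U. The documents give no value for U, and the SAP plans no related-event count.

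**3. What the listings show**

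The listings concerned are 16.2.7.1 to 16.2.7.6, which is six. The study closed with 25 women enrolled (SAP section 4.5), so at most 25 subjects appear.

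- SAP section 9.4 says that all study data will be listed, and the recorded causality term is study data.
- Where the SAP wants derived content in a listing, it usually names it: changes from baseline and nadir for target lesions (section 14), the treatment-emergent flag (15.3), change in performance status (15.5), and medications before versus during dosing (section 12). Section 15.3 names no derived two-level relatedness variable.
- Each adverse event listing carries onset and resolution dates. SAP section 13.2 lists dosing days and times, and listings 16.2.5.1 and 16.2.5.2 hold the injection and diary records.

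The recorded term is thus the more natural reading. Even with the grouped label, onset can be compared with dosing, subject by subject.

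**4. Reporting of serious events**

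Under protocol section 5.9.5, serious events go to pharmacovigilance within 24 hours whether or not they seem drug-related. The investigator notifies the ethics committee within 72 hours, again with no causality condition.

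One route does depend on causality: serious events up to 60 days after the last dose are reported if the investigator suspects a link. For subjects treated in Period 2, routine collection ends at the Safety Follow-up Visit, four weeks after the last treatment. The causality-dependent stretch is therefore about 60 − 28 = 32 days. The condition there is the investigator's suspicion, and neither document ties it to the grouped label.

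**The case for a change.** The strongest case for a change has three parts.

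First, SAP section 15.1 prescribes the grouping for data analysis, and section 9.4 allows exceptions to the general listing rule, so a programmer could print the grouped label. That stands: the SAP does not name the term, and it does not say whether the column is split by drug. If it happened, the listings would lose the investigator's own distinction, although the dates would still allow a reader to recover the timing.

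Second, ratings are made for each drug, and the wording on other drugs does not exclude the partner study drug. An event compatible in time with both could be 'unlikely' for each, and so 'not related' to both. That is a fair reading of the text. It bears on where the scale is cut, which would matter for a tabulated related-event rate. The SAP plans none.

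Third, the mapping covers reporting of serious events, and both the 60-day rule and suspected unexpected serious reactions (protocol section 8.2.1) depend on suspected causality. The link is left undefined, which also stands. But no step in the documents turns an 'unlikely' rating into a missed report, and the 72-hour notice to the ethics committee does not depend on the rating.

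**Conclusion.** No change to the plan is called for. The tension between the Table 14 definitions and the mapping is real but ordinary: it is an explicit, consistently stated split of four terms into two, with the same looseness on the 'possibly related' side. The 'unlikely' step changes the number of events labelled related by zero, and no analysis uses that number.

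The remaining gap is which relatedness term the listing column shows. It touches six listings and at most 25 subjects. Analysts can fill it sensibly by showing the investigator's recorded term, for each drug where it was captured. Doing so alters no result or conclusion of a listings-only report.

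This rests on three assumptions: the case report form holds the four-level term, as the requirement in protocol section 5.9.1 to record relationship implies; the onset and dosing listings are produced as SAP sections 13.2 and 15.3 describe; and no related-event summary is added later. If one were added, the cut between 'unlikely' and 'possibly' would affect the figure and would need to be stated with it. How many events are rated 'unlikely' cannot be estimated from the documents.

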5.9.4. Criteria for Defining the Severity of an Adverse Event

Table 15. The severity of all AEs should be graded according to the NCI-CTCAE Version 4:

Grade	Assessment Standard
1 – Mild	Does not hamper daily activities
2 – Moderate	Hampers daily activities
3 – Severe	Makes daily activities impossible
4 – Life-Threatening	Imminent risk of death
5 – Death	Death

5.9.5. Reporting of Serious Adverse Events (SAEs)

AEs meeting the criteria as an SAE must be reported to ProductLife Pharmacovigilance within 24 hours of becoming aware of its occurrence even if the SAE does not appear to be study drug-related. An SAE Form and any related eCRFs must also be completed by the Investigator and faxed or emailed to ProductLife Pharmacovigilance within 24 hours:

SAFETY REPORTING Contact: ProductLife Pharmacovigilance

- Email: [contact]
- [contact]

Within the following 48 hours, the Investigator shall provide further any additional information regarding the SAE and a written narrative of the event. Follow-up including additional information,

complications or worsening of the initial SAE must be reported as follow-up to the original episode within 24 hours of the Investigator receiving the information. Any SAEs experienced up to 60 days after last administration of study drug should be reported if the Investigator suspects a causal relationship to the study drug. Deaths or congenital abnormalities brought to the attention of the Investigator at any time after administration of study drug and considered by the Investigator to be possibly related to study drug, should be reported to the Sponsor.

The Investigator must also notify the reviewing IEC/IRB in writing as soon as possible but no later than 72 hours of knowledge of an SAE. Documentation of IEC/IRB notification and receipt will be kept in the Investigator's study file.

Expedited regulatory reports will be submitted by Xenetic or designee to the regulatory authorities in accordance with specific country requirements.

